**Secondary:**

- Change in HbA1c from baseline to 12 weeks (+/-2 weeks) post-discharge
- Change in fasting plasma glucose (FPG) from baseline in DOS vs ESC
- % of patients achieving HbA1C 7% in DOS vs ESC
- % of patients achieving HbA1C 6.5% in DOS vs ESC
- % of patients achieving individualized HbA1c target in DOS vs. ESC: HEDIS HbA1c target (<8% if age  $\geq$  65 years or known history of ischemic vascular disease, heart failure, advanced kidney disease [eGFR <30], dementia, proliferative retinopathy/blindness, advanced neuropathy [history of ulcer or amputation] or history of severe hypoglycemia; otherwise goal is <7%)
- Proportion of patients with accurate and complete discharge orders for insulin and related supplies.
- Adherence to glargine U300 (>80% of doses) at 2, and 24 weeks
- Proportion of patients who remain on glargine U300 at 24 weeks
- Mean dose of glargine U300 at 2 and 24 weeks
- Proportion of patients who follow up with their primary care provider within 2, 6 weeks of discharge
- Incidence of documented symptomatic (BG <54 mg/dl) hypoglycemia

**Analysis:** Outcomes will be further analyzed by type of diabetes, pre-admission therapy, and bolus insulin requirements.

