#### **D.2.g. Program Completion**

Participants will receive an order to complete the HbA1c at 12 and 24 weeks at any OSU lab. A reminder letter will be sent 1 week prior to the date and a phone call reminder will occur 2 days before the visit. Study team will complete the 12 week and 24 week call and search the electronic medical record and primary provider's chart for HbA1c and healthcare utilization at 12 and 24 weeks.

**E. Study Drug:** Patients in both groups will be provided standard of care insulin therapy throughout the study, including insulin glargine (TOUJEO® U300) plus additional background therapy (non-insulin and prandial insulin therapies), based upon discharge team preference. The starting dose will be determined during hospitalization from the dose of glargine/detemir U100 in a 1:1 dose conversion. Upon discharge, standard titration instructions (every 4 days) will be implemented in the DOS group but will be left to the discretion of the discharge team in the ESC group.

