### **F.2.b. Basal insulin titration**

The patient will receive instructions via the discharge order set and nurse to adjust the U300 basal insulin dose 2 unit Q4 days for glucose >130 mg/dl, provided no values <80 mg/dl.

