**Secondary:**

- Difference in the change in HbA1c from baseline to 12 weeks (+/-2 weeks) post-discharge (%, mmol/l)
- Difference in the change in HbA1c from baseline to 12 and 24 weeks (+/-2 weeks) post-discharge (%, mmol/l)
- Difference in the change in fasting plasma glucose (FPG) from baseline to 12 and 24 weeks in DOS vs ESC (mg/dl)
- Difference in the % of patients achieving HbA1C 7% in DOS vs ESC (12, 24 weeks)
- Difference in the % of patients achieving HbA1C 6.5% in DOS vs ESC (12, 24 weeks)
- Difference in the % of patients achieving individualized HbA1C target in DOS vs ESC (12, 24 weeks)
- Difference in the proportion of patients with accurate and complete discharge orders for basal insulin and related supplies. (%)
  - Assessed as complete dose, quantity dispensed, adequate refills (separate for basal and prandial insulin), and correct prescription for pen needles (presence, quantity, adequate refills), no jargon
- Difference in the proportion of patients with accurate and complete discharge orders for prandial insulin and related supplies. (%)
  - Assessed as complete dose, clear dosing instructions, quantity dispensed, adequate refills, and correct prescription for pen needles (presence, quantity, adequate refills), no jargon
- Difference in the proportion of patients with a discharge prescription for glucose monitoring supplies (%)
- Difference in adherence to glargine U300 (% taking >80% of doses) at 2, and 24 weeks
- Difference in the proportion of patients who remain on glargine U300 at 24 weeks (%)
- Difference in the mean dose of glargine U300 at 2 and 24 weeks (units)
- Difference in the frequency of glucose monitoring at 2 and 24 weeks (times per day)
- Difference in the proportion of patients who follow up with their primary care provider or endocrinologist within 2, 6 weeks of discharge (%)
- Difference in the incidence of documented symptomatic (BG <54 mg/dl) hypoglycemia (%)

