#### H.2.d. Secondary Aims:

- Determine whether DOS is associated with lower HbA1c at 12 months compared to ESC.
- Determine whether the DOS in conjunction with nurse supported self-titration of basal insulin glargine U300 is associated with improved persistence with insulin therapy, adequate dose titration, and use of self-monitored blood glucose.
- Determine whether the DOS is associated with improved discharge instructions and processes of care for insulin-requiring patients. This will be measured in terms of clarity of instructions, adequacy and completeness of prescriptions for insulin and diabetes supplies, and follow-up plan.

Each of these secondary outcomes will be binary (e.g., adequate vs. inadequate dose titration). Missing values of the outcomes will be imputed using treatment group and baseline covariates. The difference in proportions between treatment groups will be computed for each data set and the results will be combined using Rubin's rules to obtain a final two-sample test of proportions.

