 Call your healthcare provider if you have recurrent high (above 250 mg/dl) blood sugars for more than 3 days in a row, or if you have glucose readings over 250 mg/dl with new symptoms such as nausea, vomiting, or dizziness.		
Patient Instructions		
 Your target glucose is *** mg/dl fasting and under *** mg/dl nonfasting  <Note: Typical blood sugar goals for many people are 80-130 mg/dl in the mornings (fasting) and less than 180 mg/dl throughout the rest of the day>		
 Instructions for Managing Your Diabetes at Home	[Attachment]	
Diabetes Medication and Supply: Note: U100 Insulin vials contain 1000 units, U100 pens contain 300 unit/pen, glargine U300 contains 450 unit/pen, degludec U200 contains 600 unit/pen, lispro U200 contains 600 unit/pen. [each prescription option is paired with U100 0.3 or 0.5 ML syringe or pen needles as appropriate]		
➤ Basal Insulin	 [Example Drop-down Menu:]  Insulin Glargine 300 unit/ml pen *** units every day.  Increase *** unit every 4 days until AM (fasting) glucose is under *** mg/dl, provided that you have no glucoses under 80 mg/dl, do not go above *** unit per day.	
➤ Glargine U100 Solostar pen and pen needles ➤ Glargine U300 Solostar pen and pen needles ➤ Detemir U100 FlexTouch pen and pen needles ➤ Degludec U100 FlexTouch pen and pen needles ➤ Degludec U200 FlexTouch pen and pen needles ➤ Glargine U100 vial and syringes		

 
➤ Detemir U100 vial and syringes
 
➤ NPH U100 vial and syringes
 
	 [Cardiac surgery patients]: Reduce dose by 2 unit every day that you wake up with a glucose less than 100 mg/dl or if you have any glucose levels under 80 mg/dl.  No titration Dispense: 3 prefilled pens; Refills: 1  Pen needle 31 G x 4 mm For use with insulin once daily Dispense: 50; Refills: 1														

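### The U300 dose endpoint is compared as a raw mean with no adjustment for starting dose, which costs precision, mainly at week 2

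*Combined protocol and SAP*

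**What the plan says.** The secondary endpoints in H.2.b include "Difference in the mean dose of glargine U300 at 2 and 24 weeks (units"; the endpoint list in the opening summary has the same quantity, "Mean dose of glargine U300 at 2 and 24 weeks". Neither refers to a starting dose. Other continuous endpoints in the H.2.b list are written as changes, for example "Difference in the change in fasting plasma glucose (FPG) from baseline to 12 and 24 weeks in DOS vs ESC (mg/dl".

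Section E (Study Drug) sets the dose at entry: "The starting dose will be determined during hospitalization from the dose of glargine/detemir U100 in a 1:1 dose conversion". Eligibility requires basal insulin of at least 10 units/day (D.2.b) or more than 10 (Table 6), with no upper limit. D.2.d stratifies randomisation by pre-admission insulin use, while Human Subjects A.1.a says by race. These two statements need reconciling, but neither makes starting dose a stratification factor.

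In the DOS arm, F.2.b tells patients to "adjust the U300 basal insulin dose 2 unit Q4 days for glucose >130 mg/dl, provided no values <80 mg/dl". In the ESC arm, titration is left to the discharge team (section E, Table 7).

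On analysis, H.2.c uses insulin dose as a baseline covariate, but for HbA1c only. H.2.d treats the secondary-aim outcomes as binary, giving "adequate vs. inadequate dose titration" as its example, and specifies a two-sample test of proportions. H.1.a assigns longitudinal outcomes to mixed models, with HbA1c as its example. It does not name dose.

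**The concern.** Dose titration is a stated secondary aim, and it is one route by which DOS is expected to lower HbA1c. The work plan in section J foresees a manuscript covering titration. The week-2 dose is the starting dose plus at most a few small steps. A raw mean therefore carries the full between-patient spread in starting dose as noise around a small signal. The likely result is an inconclusive week-2 comparison even if patients titrated as instructed, and that could be reported as evidence that the mechanism did not operate. The plan gives no model for mean dose that would remove this noise.

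**Working it through.** **The plan's own figure.** The only computed sample size is for HbA1c (H.2.a), and it is used here only as the source of n per arm. With σ = 2.2, ρ = 0.25, R² = 0.5, Δ = 0.8, two-sided α = 0.05 and 80% power:

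n = 4 × 2.2² × 0.75 × 0.5 × (1.960 + 0.842)² / 0.8² = 89.04, stated as 89. Then 89 / 0.80 = 111.25, stated as 111.

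The figures reproduce. The 89 are those with 24-week data, so numbers at week 2 should lie nearer 111.

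**Titration ceiling under F.2.b.**
- Day 14: floor(14/4) × 2 = 3 × 2 = 6 units per DOS patient.
- Day 168: (168/4) × 2 = 84 units.

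**Chance imbalance in mean starting dose.** SE = SD × √(2/n), and the 95% limit is 1.96 × SE. The documents give no SD for dose, so all SDs below are assumptions.

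| Assumed SD (units) | 95% limit, n = 111 | 95% limit, n = 89 | P(imbalance > 6), n = 111 / 89 |
|---|---|---|---|
| 10 | ±2.6 | ±2.9 | under 0.1% / under 0.1% |
| 20 | ±5.3 | ±5.9 | 2.5% / 4.5% |
| 30 | ±7.9 | ±8.8 | 13.6% / 18.2% |
| 40 | ±10.5 | ±11.8 | 26.4% / 31.7% |

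The limit equals 6 when SD = 6 / (1.96 × √(2/n)), which is 22.8 for n = 111 and 20.4 for n = 89.

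**Power for a true 3-unit difference at week 2** (half the ceiling taken in DOS, none in ESC), two-sided 5%, normal approximation, both tails counted: power = Φ(3/SE − 1.96) + Φ(−3/SE − 1.96).
- Raw mean, SD 20, n = 111: SE = 2.68, power 20%.
- Raw mean, SD 40, n = 89: SE = 6.00, power 8%.
- Change, SD 5, n = 111: SE = 0.67, power 99%.
- Change, SD 8, n = 89: SE = 1.20, power 71%.
- For contrast, raw mean with SD 10: power 61% (n = 111) or 52% (n = 89).

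**What the change SDs imply.** If the dose SD is the same at both times, Var(change) = 2 × SD² × (1 − r). Raw SD 20 with change SD 8 gives r = 1 − 64/800 = 0.92. Raw SD 40 with change SD 5 gives r = 1 − 25/3200 = 0.99. The 71–99% therefore presupposes that baseline dose predicts week-2 dose very closely.

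**The case against.** The strongest reply is that randomisation already protects the comparison. The raw difference in means is unbiased, and its standard error already allows for chance imbalance in starting dose. This stands. A reader might infer that imbalance would create a spurious titration effect beyond the nominal 5% error rate, but nothing in the design supports that.

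Second, the size depends on SDs that the documents do not give. This also stands. A reader might infer that chance differences will exceed what titration can add. At SD 20 the 95% limit is still below 6 units, and at SD 10 it is about half that.

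Third, 6 units is a per-patient ceiling by day 14, not a cap on the difference between arms. ESC doses may rise or fall at the team's discretion. No window is stated for the week-2 contact, and a contact on day 16 would allow a fourth step (8 units). The order-set mock-up leaves the step size blank and offers a no-titration option, which should be reconciled with F.2.b.

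Fourth, H.2.a says openly that the trial is sized for the primary endpoint alone. That excuses low power, but not the omission of a covariate that costs almost nothing. H.2.c itself justifies covariates by precision rather than by imbalance.

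Fifth, the mixed-model sentence in H.1.a could be read as covering dose. Even so, the endpoint lists only weeks 2 and 24, and a model of those two values without a baseline dose leaves the spread in starting dose in the error.

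Sixth, the background section on insulin titration says doses are often optimised before discharge. Changes between randomisation and discharge would weaken the link between baseline and week-2 dose, so the real gain may be smaller than the change-score figures suggest.

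**Conclusion.** The point holds as one of precision and interpretability, not validity. No adjustment for starting dose is specified for the dose endpoint, and under the F.2.b rule the week-2 raw mean mostly reflects starting dose. Chance imbalance exceeds 6 units at the 95% limit only if the starting-dose SD is above about 20 to 23 units. Under the assumed SDs, power for a 3-unit difference is about 8–20% on the raw mean against 71–99% on change. If the SD is nearer 10, the raw comparison is far less weak, although adjustment would still help.

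A reader might extend the criticism equally to week 24. The documents do not support that: the rule permits up to 84 units by then, so titration can outweigh the spread in starting dose and the issue is minor.

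A reader might also infer that mean dose is meant to stand in for the binary adequacy outcome that H.2.d gives as an example. No section says so. How adequacy is to be defined is a separate question, and this point does not rest on it.

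**What to change.** In H.2.b, and in the matching line of the opening summary's endpoint list, specify that U300 dose at 2 and 24 weeks is compared between arms with baseline basal dose as a covariate, by ANCOVA or a mixed model. Analysing change from baseline with the same covariate gives the same treatment estimate. Report raw means by arm descriptively. Adjustment is safer than an unadjusted change score, because it does not lose precision if baseline and follow-up dose turn out to be weakly correlated.

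Use the basal dose recorded at or before randomisation, so that the covariate cannot be affected by the order set. Confirm that this dose is captured as its own field: D.2.e lists only total units per day, for the discharge regimen, and Table 9 has no explicit starting-dose item.

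The cost is a sentence or two of SAP text and one data field. Visits, sample size and the primary analysis are unchanged.

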**D.1.b. Secondary Aims:**

- Evaluate the efficacy of a diabetes focused inpatient discharge order set (DOS) on reducing HbA1c at 12-24 weeks compared to enhanced standard care (ESC) among hospitalized basal insulin requiring patients with uncontrolled diabetes.
- Determine whether the DOS in conjunction with nurse supported self-titration of basal insulin glargine U300 is associated with improved persistence with insulin therapy, adequate dose titration, and use of self-monitored blood glucose.
- Determine whether the DOS is associated with improved discharge instructions and processes of care for insulin-requiring patients. This will be measured in terms of clarity of instructions, adequacy and completeness of prescriptions for insulin and diabetes supplies, and follow-up plan.

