**Table 7. Intervention procedures**

	Enhanced Standard Care	Discharge Order Set
Diabetes Education	Basic survival skills	Basic survival skills
Discharge orders	Per primary team: medication reconciliation, prescriptions and instructions, follow-up appointments	Discharge order set in addition to primary team
Patient Care Resource Manager	Yes	Yes
U300 glargine at discharge	Yes	Yes
U300 glargine titration	Per primary team	Yes
Follow-up	Coordinator call to assess adherence, outcomes	Nurse call to confirm titration

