**Table 8. Diabetes Order Set Summary**

Standard Elements		
Diabetes-specific elements	Detail	Prescriber Guidance
Diet	Choice of consistent (defaults to 45 or 60 gram/meal) or flexible carbohydrate	Selection criteria for flexible carb diet.
Follow-up and referrals	Choice of primary care or endocrinology (call for appointment for *** weeks, appointment has been made for ***) Diabetes education (general education or survival skills)	Only local patients should be referred to OSU.
Patient instructions	Call provider for hypoglycemia Call provider for hyperglycemia Bring glucose log to appointment Glucose targets Home diabetes management attachment	Identification of glucose targets
Insulin prescriptions	Each insulin is presented as a panel, linked to pen needle or syringe as appropriate Each insulin Rx defaults to 3 pen or 1 vial with 1 refill Insulins categorized by basal, prandial set meal dose with correction, or prandial flexible meal dose with correction	Number of units per pen or vial Syringe size Titration options for basal insulin Selection criteria for flexible meal dosing Correction dosing from pick list of low, standard, or high doses
Glucose Monitoring supplies	Panels categorized by frequency of monitoring Each panel contains glucometer, test strips, lancets, alcohol wipes Prescriptions default to dispense appropriate number of supplies with 1 refill	Guidance on monitoring frequency
Other DM supplies	Ketone strips Glucagon	Selection criteria provided for each

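### The only listed hypoglycaemia endpoint needs a glucose reading, and DOS is meant to increase testing, so the between-arm comparison can reflect detection as well as risk

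*Combined protocol and SAP*

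**What the plan says.** The secondary endpoints in section H.2.b include "Difference in the incidence of documented symptomatic (BG <54 mg/dl) hypoglycemia", expressed as a percentage. The synopsis has the same item: "Incidence of documented symptomatic (BG <54 mg/dl) hypoglycemia". Neither list has another hypoglycaemia endpoint.

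The same plan intends DOS to change how often glucose is measured:

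- A secondary aim in D.1.b, repeated in H.2.d, is that DOS brings "improved persistence with insulin therapy, adequate dose titration, and use of self-monitored blood glucose".
- On monitoring supplies, Table 8 states: "Each panel contains glucometer, test strips, lancets, alcohol wipes". The Appendix adds default quantities and a choice of testing frequency. Under enhanced standard care (ESC), Table 7 leaves discharge orders to the primary team.
- DOS titration runs on readings (F.2.b): "2 unit Q4 days for glucose >130 mg/dl, provided no values <80 mg/dl". In ESC, titration is left to the primary team.
- H.2.b lists, as between-arm endpoints, monitoring frequency at 2 and 24 weeks and also "Difference in the proportion of patients with a discharge prescription for glucose monitoring supplies".

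For follow-up, Table 7 gives ESC a "Coordinator call to assess adherence, outcomes" and gives DOS a nurse call about titration. H.2.d analyses binary secondary outcomes by a two-sample test of proportions after multiple imputation and mentions no allowance for testing.

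Severe hypoglycaemia is collected as an adverse event under a clinical definition that needs no glucose value (Data and Safety Monitoring Plan, item 2). No comparison of it between arms is stated.

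**The concern.** A between-arm comparison of an event is fair only if the event is about equally likely to be captured in each arm. Here capture depends on whether the patient tests during symptoms, which the intervention is designed to influence. Imputation does not help: on this definition, an episode without a reading would be recorded as no event rather than as a missing value.

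The trial tests insulin self-titration in recently discharged patients, and the Background says its feasibility in such patients is unclear. Hypoglycaemia is the natural counterweight to any HbA1c gain. If more events are documented in DOS, the endpoint alone cannot show whether that is risk, detection or both. A true reduction in DOS could also be hidden.

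**Working it through.** **Figures in the plan.** The documents give no expected hypoglycaemia incidence, testing rate or documentation rate, so there is no stated figure for this endpoint to reproduce. The group size used below comes from H.2.a and does reproduce: 4 × 2.2² × (1 − 0.25) × (1 − 0.5) × (1.960 + 0.842)² / 0.8² = 89.04, stated as 89 per group. Also, 89 / 0.8 = 111.25, stated as 111. Neither is in dispute.

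**Model (illustration; every rate is an assumption).** Let p be the true proportion of patients with a symptomatic episode below 54 mg/dl, and q the probability that such a patient has one documented. Then

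observed incidence = p × q, and observed RR = true RR × (q in DOS / q in ESC).

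**No true difference.** Take p = 20% in both arms and q = 0.9 in DOS. The last column is the probability that a pooled two-proportion z-test (two-sided 0.05, 89 per arm) declares a difference.

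| q in ESC | DOS observed | ESC observed | Difference | RR | Rejection |
|---|---|---|---|---|---|
| 0.9 | 18% | 18% | 0 points | 1.00 | 5.0% |
| 0.8 | 18% | 16% | 2 points | 1.12 | 6.4% |
| 0.7 | 18% | 14% | 4 points | 1.29 | 11.2% |
| 0.6 | 18% | 12% | 6 points | 1.50 | 20.1% |
| 0.5 | 18% | 10% | 8 points | 1.80 | 33.6% |

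Over p from 10% to 30% and q in ESC from 0.8 to 0.5, the RR runs from 1.12 to 1.80 and rejection from 5.7% to 50.2%.

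**True benefit of DOS.** Suppose 15% versus 20%, a true RR of 0.75.

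- q of 0.9 versus 0.7: 13.5% versus 14.0%, RR 0.96. The benefit nearly disappears.
- q of 0.9 versus 0.6: 13.5% versus 12.0%, RR 1.13. The sign reverses.

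Reversal needs a ratio of q above 1 / 0.75 = 1.33. Here 0.9 / 0.6 = 1.5 exceeds it, and 0.9 / 0.7 = 1.29 does not.

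**Several episodes per patient.** If the endpoint is a per-patient proportion, one documented episode is enough. With capture probability c per episode and three independent episodes (also an assumption), q = 1 − (1 − c)³. At p = 20% in both arms:

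- c of 0.9 versus 0.7: q = 0.999 versus 0.973, difference 0.20 × 0.026 = 0.5 points.
- c of 0.9 versus 0.6: q = 0.999 versus 0.936, difference 0.20 × 0.063 = 1.3 points.

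**Against sampling error.** For 18% versus 12% at 89 per arm, the standard error is √[(0.18 × 0.82 + 0.12 × 0.88) / 89] = 5.3 points.

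**The case against.** The strongest reply is that ESC is also monitored. ESC patients are told to keep a glucose and insulin diary (F.1.a), as DOS patients are (F.2.a). In Table 9, the rows for monitoring instructions at baseline and for hypoglycaemia and diary review at 2, 6, 12 and 24 weeks carry no arm restriction, whereas the nurse-counsellor row is marked as DOS only. Both arms receive survival skills education. The Appendix provides for a meter only where the patient lacks one, so some patients already own one. Symptoms can also prompt a test in either arm.

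All of this stands, and it rules out some stronger inferences. A reader might infer that ESC patients without a new prescription cannot have a documented event; existing meters and readings taken elsewhere contradict that. A reader might infer that DOS will necessarily show more hypoglycaemia; more testing in DOS is a hypothesis of the trial, and without it the bias is small. A reader might infer that nothing else is recorded on hypoglycaemia; severe events and the Table 9 review show otherwise.

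The reply also notes that the size is wholly assumed, shrinks with repeated episodes, and is modest beside the sampling error of a secondary endpoint for which the study is not powered. That is fair. But sampling error does not remove a systematic difference in capture, and the plan states no reading-independent comparison. The severe-event definition is narrow, being tied to seizure or haemodynamic compromise.

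**Conclusion.** The concern holds in a limited form. The only listed hypoglycaemia endpoint depends on a reading, and DOS is meant to make readings more frequent. If it does so, the planned comparison can mix detection with risk, with over-counting in DOS the likely direction.

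The size cannot be determined from the documents. Under the assumptions shown, with equal true risk of 20%, the spurious difference ranges from 2 to 8 points if each affected patient has one chance of documentation. For the two capture gaps worked through with three episodes, it is about 0.5 and 1.3 points. The symptom requirement and the monitoring common to both arms push towards the lower end. The sign reversal requires a wide capture gap and should be read as a possibility, not a prediction. The primary HbA1c analysis and the sample size are unaffected.

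**What to change.** Keep the documented endpoint below 54 mg/dl and make three additions:

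1. A supportive endpoint: any symptomatic hypoglycaemia reported at the 2, 6, 12 and 24 week contacts, with or without a glucose value, asked with the same scripted question in both arms.
2. A by-arm report of this endpoint and of severe hypoglycaemia as defined in the Data and Safety Monitoring Plan, set next to the monitoring-frequency endpoint.
3. A sentence in the analysis plan that the between-arm hypoglycaemia conclusion will not rest on the reading-dependent count alone.

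Do not use events per 100 readings as a correction. The denominator is a post-randomisation quantity that DOS is meant to raise. With equal event counts and twice the readings, the DOS rate would halve, and extra routine tests could make DOS look falsely safe.

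The cost is one scripted question and field at contacts that Table 9 already uses for hypoglycaemia review, one endpoint line and one table. The script matters because the narrative for the 2 and 6 week contacts (F.1.b, F.2.c) does not mention hypoglycaemia. The downside is that a definition without a reading is less specific. It is also open to reporting differences, because patients know their care and are questioned by a nurse in DOS and a coordinator in ESC. It therefore supports the documented endpoint and does not replace it.
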